16.3 Physical/Neurological Examinations

The occurrence of a physical examination (yes/no) and the date performed and the neurological examination date along with the system and results will be listed by the participant.

16.4 Vital Signs

Vitals for the following parameters - respiratory rate (breaths/minute), oral temperature (degrees C), supine heart rate (beats/minute), supine systolic blood pressure (mmHg), supine diastolic blood pressure (mmHg), standing heart rate (beats/minute), standing systolic blood pressure (mmHg), standing diastolic blood pressure (mmHg), – are collected at Screening and on Days -7, -1, 1, 7, 14, and 28 for Part A, and for Part B an additional collection will be made on Days 21, 35 and 42. Descriptive summaries of observed values and changes from baseline will be provided for vital sign parameters along with body weights by scheduled assessment time points for Part A and Part B separately. Additionally, the number and percentage of participants with PCS and potentially clinically significant change (PCSC) values will be summarized for such occurrence at any post-baseline visit. Potentially clinically significant values will be identified for vital sign parameters as outlined in Table 6.

Table 6 Potentially Clinically Significant Values and Change for Vital Sign Parameters

Vital Sign	Units	Criteria for PCS Values (Observed values)		Criteria for PCSC values (Change from Baseline values)	
		High	Low	Increase	Decrease
Heart rate (supine and standing)	Beats/min	>120	<40	NA	NA
Systolic Blood Pressure (supine and standing)	mmHg	>180	<90	≥30	≥30
Diastolic Blood pressure (supine and standing)	mmHg	>110	<50	≥20	≥20
Supine - Standing Systolic Blood Pressure	mmHg	≥20			
Supine – Standing Diastolic Blood Pressure	mmHg	≥10			
Orthostatic hypotension: supine – standing SBP and DBP	mmHg	SBP ≥20 and DBP ≥10			
Possible Orthostatic hypotension: supine – standing SBP and DBP	mmHg	SBP ≥20 or DBP ≥10			

The orthostatic vital sign - the change from supine to standing (Supine – Standing) in heart rate, systolic and diastolic blood pressure – will be summarized by scheduled assessment timepoint, at 1 and 3 minutes.

Any vital signs result considered clinically significant by the investigator will be captured as adverse events, and hence will show up in AE displays. All vital sign assessments along with PCS will be listed.

16.5 12-Lead Electrocardiogram

Supine 12-lead ECGs will be performed in triplicate, and are collected on screening, days -1, 1, 7, 14, and 28 for Part A whereas for Part B it is performed on days -1, 14, 28, and 42. The following ECG parameters will be listed for each participant: heart rate (beats per minute), PR (msec), QRS (msec), QT (msec), and QTcF (msec).

The average of the triplicate values will be used in the summary, including baseline ECG values. The precision on averages is to keep only 2 decimal places. The observed value at each time point and change from baseline at each post-baseline scheduled time point will be summarized. Each ECG is evaluated as 'normal', 'abnormal, not clinically significant' and 'abnormal, clinically significant'; the number and percentage of participants with at least one of the triplicate values in the categories of normal, 'abnormal, clinically significant' and 'abnormal, not clinically significant' will be provided at baseline and each post-baseline scheduled assessment time point.

The number and percentage of participants with PCS and PCSC values will be summarized for such occurrence of baseline and at any post-baseline visit. Potentially clinically significant values will be identified for ECG parameters as outlined in Table 7. A listing of ECG and QTcF PCS values will be provided.

Table 7 Potentially Clinically Significant Values and Change for ECG Parameters

ECG	Units	Criteria for PCS Values (Observed values)		Criteria for PCSC values (Change from Baseline)	
		High	Low	Increase	Decrease
QTcF Interval	msec	>450 but <=480 >480 but <=500 >500	NA	>=30 to 60 >60	NA

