Vital signs ^d	X	X	X	X		X	X		X
Physical examination ^e	X	X	X				X		
EEG ^f	X								
12-lead ECG ^g	X		X	X		X	X		X
C-SSRS ^h	X	X	X	X		X	X		X
Clinical laboratory tests ⁱ	X		X			X	X		X
Alcohol test ^j	X	X							
Urine drug test	X	X	X	X		X	X		
FSH test ^k	X								
Pregnancy test ^l	X		X				X		X
Serology test ^m	X								
Participant training ^o		X	X						

Study Period	Screening		Baseline		Treatment			Follow Up	
	D -21 to D -8	D -7 (±1 d)	D -1	D 1	D 4 ^a	D 7 (±1 d) or ET	D 14	D 21 ^a (±1 d)	D 28 (±2 d)
Remote assessments [†]				X					
IP self-administration ^u				X (once daily)					
IP dispensation ^v				X		X			
IP accountability ^w				X					
Safety telephone call					X			X	
TEAEs/SAEs				X					
Concomitant medications ^x				X					

Abbreviations: C-SSRS = Columbia–Suicide Severity Rating Scale; d = days; ECG = electrocardiogram; EEG = electroencephalogram; ET = early termination; FSH = follicle stimulating hormone; IP = investigational product; [REDACTED] SAE = serious adverse event; TEAE = treatment-emergent adverse events; [REDACTED]

- Note: In the event of early termination, efforts should be made to collect the Day 14 visit assessments. When scheduled for the same time point, procedures should be performed in the following order: vital signs, ECG, blood draws, morning meal, IP dosing, then any scheduled postdose and/or [REDACTED]. In the setting of public health advisories or similar risks to patient safety, assessments scheduled to be conducted at the study site may be performed via telephone/video if feasible. For assessments that cannot be conducted by phone or video, an in-home visit may be conducted.
- a Day 4 and Day 21 visits will occur via scheduled telephone calls.
 - b Both participants and study partners are to be consented during the Screening Period.
 - c In addition to full medical history, all nonpharmacological methods (eg, psychosocial, psychotherapeutic) used to treat or prevent neuropsychiatric, functional, and cognitive manifestations of PD are to be recorded.
 - d Vital signs to include temperature, respiratory rate, heart rate, and blood pressure. Heart rate and blood pressure to be collected in supine position and standing position at all scheduled time points.

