 - d. Other medications given at doses, frequencies, or in combinations that are likely, in the opinion of the investigator, to have a deleterious effect on cognitive performance, based on the 2019 American Geriatrics Society Updated Beers[®] Criteria for

Potentially Inappropriate Medication Use in Older Adults ([American Geriatrics Society 2019](#))

- e. Prescribed cannabis or other THC-containing substances
12. Have an alcohol or drug use disorder within the past 12 months as per DSM-5 criteria
 13. Have a history of seizures or epilepsy, with the exception of a single episode of febrile seizures in childhood
 14. Have current or recent suicidality, defined as follows:
 - a. Suicidal ideation within the past month, as evidenced by a score of 4 (active suicidal ideation with some intent to act, without specific plan) or 5 (active suicidal ideation with specific plan and intent) on the screening or baseline Columbia–Suicide Severity Rating Scale (C-SSRS)
 - b. Suicidal behavior within the past year, as evidenced by a "Yes" on any of the 5 C-SSRS Suicidal Behavior Items (actual attempt, interrupted attempt, aborted attempt, preparatory acts, or behavior) on the C-SSRS during Screening or Baseline
 - c. Participant presents a serious risk of suicide in the opinion of the investigator.
 15. Have any of the following clinically significant medical conditions:
 - a. Any clinically significant finding on 12-lead ECG during Screening or Baseline
 - b. Supine vital signs outside of the following ranges during Screening or Baseline; vital sign measurements may be repeated once if initial values exceed these ranges:
 - Heart rate <50 or >100 bpm
 - Systolic blood pressure <100 or >160 mmHg
 - Diastolic blood pressure <60 or >100 mmHg
 16. Have significant hepatic, renal, cardiovascular, pulmonary, gastrointestinal, hematological, immunologic, ophthalmologic, metabolic, or oncological disease
 17. Have a history, presence, and/or current evidence of serologic positive results for HIV-1 or HIV-2
 18. Have a positive pregnancy test or be lactating at Screening or Day -1
 19. Be investigative site personnel, sponsor personnel, or an immediate member of their family (spouse, parent, child, or sibling whether biological or legally adopted)

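### The post-baseline orthostatic hypotension count has no stated baseline count or split by baseline status, so it mixes pre-existing postural drops with new ones

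*SAP*

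**What the plan says.** **Counting rule.** SAP 16.4 says that PCS and "potentially clinically significant change (PCSC) values will be summarized for such occurrence at any post-baseline visit". The quoted words name the change criteria, but the same sentence covers observed-value PCS criteria, so it governs the orthostatic rows.

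**Criteria.** Table 6 has four supine-minus-standing rows. Two are composites: orthostatic hypotension ("SBP ≥20 and DBP ≥10") and possible orthostatic hypotension ("SBP ≥20 or DBP ≥10"). All four sit in the observed-value columns, and their change-from-baseline cells are empty. Supine and standing SBP and DBP do have change-from-baseline limits.

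**Neighbouring rule.** For ECG, SAP 16.5 says that "PCS and PCSC values will be summarized for such occurrence of baseline and at any post-baseline visit".

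**Eligibility.** Protocol 8.2, exclusion 15b, rejects "Supine vital signs outside of the following ranges during Screening or Baseline". No criterion sets a standing or orthostatic limit. Exclusions 2 and 16 leave significant comorbid or cardiovascular disease to broad wording and the investigator's judgement.

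**Data available.** Footnote d of the protocol's schedules of assessments has "Heart rate and blood pressure to be collected in supine position and standing position at all scheduled time points". That includes Screening, Day -7, Day -1 and Day 1, when vital signs precede dosing. SAP 16.0 defines the safety baseline as the last non-missing pre-dose value.

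**The concern.** The safety question is whether postural drops appear or worsen on SAGE-718. A participant who already met the criterion before dosing, and still meets it afterwards, enters the planned count exactly as a new case would. There is no control arm to show the background rate, so each participant's own pre-dose status is the only internal reference, and this count does not use it.

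The count also pools visits during dosing with follow-up visits after dosing has ended. A reader of Tables 14.3.4.2A/B could take a background percentage for a drug signal. Equally, a few new cases could go unnoticed among pre-existing ones.

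**Working it through.** The plan gives no figure to reproduce. The main check is of the text, and the arithmetic illustrates size only.

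**1. Text, side by side**

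| Display | Reference to pre-dose status |
|---|---|
| TEAEs (SAP 16.1) | Onset on or after first dose, or worsening after it |
| ECG PCS/PCSC (SAP 16.5) | Counted at baseline and post-baseline |
| Supine and standing SBP, DBP (Table 6) | Change-from-baseline limits as well as observed limits |
| Orthostatic rows (Table 6) | Observed limits only; counted post-baseline; no baseline count stated |

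**2. Visits.** From the collection days in SAP 16.4, the post-baseline visits are:
- Part A: Days 7, 14 and 28, so n = 3. Of these, m = 2 are on treatment (Days 7, 14).
- Part B: Days 7, 14, 21, 28, 35 and 42, so n = 6. Of these, m = 4 are on treatment (Days 7 to 28).

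**3. Illustration with no drug effect.** The documents give neither rate below, so both are assumed:
- s = 0.20, the share with a persistent drop, met at every visit;
- p = 0.05, the chance per visit that any other participant meets the criterion, independent across visits.

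Planned count = s + (1 − s)[1 − (1 − p)^n]
- Part A: 0.20 + 0.80(1 − 0.95³) = 0.20 + 0.80 × 0.1426 = 31.4%, about 3.5 of 11 planned participants
- Part B: 0.20 + 0.80(1 − 0.95⁶) = 0.20 + 0.80 × 0.2649 = 41.2%, about 9.1 of 22

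New since the SAP baseline, all post-baseline visits = (1 − s)(1 − p)[1 − (1 − p)^n]
- Part A: 0.80 × 0.95 × 0.1426 = 10.8%
- Part B: 0.80 × 0.95 × 0.2649 = 20.1%

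The difference is the part already positive at baseline: 31.4 − 10.8 = 20.6 points in Part A and 41.2 − 20.1 = 21.1 points in Part B. That is about two thirds and one half of the planned counts.

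New since the SAP baseline, on-treatment visits only = (1 − s)(1 − p)[1 − (1 − p)^m]
- Part A: 0.76 × (1 − 0.95²) = 0.76 × 0.0975 = 7.4%
- Part B: 0.76 × (1 − 0.95⁴) = 0.76 × 0.1855 = 14.1%

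Stricter option, criterion met at none of the four pre-dose visits, on-treatment visits only = (1 − s)(1 − p)⁴[1 − (1 − p)^m]
- Part A: 0.80 × 0.8145 × 0.0975 = 6.4%
- Part B: 0.80 × 0.8145 × 0.1855 = 12.1%

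**4. Sensitivity to the assumptions** (s from 10% to 30%, p from 3% to 10%)

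| Count | Part A | Part B |
|---|---|---|
| Planned | 18% to 49% | 25% to 63% |
| New since SAP baseline, all post-baseline visits | 6% to 22% | 11% to 38% |
| Stricter option, on treatment | 4% to 11% | 7% to 20% |

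**5. Is a baseline column enough?** Under the same inputs, the single-visit baseline percentage is 0.20 + 0.80 × 0.05 = 24.0%. With no drug effect it still lies below 31.4% and 41.2%, because the post-baseline figure takes the worst of several visits. The split by baseline status is therefore needed as well.

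**6. Part A against Part B.** The B/A ratio is 41.2/31.4 = 1.31 as planned, 20.1/10.8 = 1.86 for new cases over all visits, and 12.1/6.4 = 1.90 for the stricter on-treatment row. Removing persistent cases leaves the part that depends on visit number. Over the same two visits (Days 7 and 14), new cases since baseline are 7.4% in both parts.

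**The case against.** **Baseline-referenced orthostatic information is already planned.** SAP 16.4 summarises the supine-to-standing difference by scheduled time point at 1 and 3 minutes, flags falls in standing SBP and DBP from baseline, and lists every value with its PCS flag. With 11 and 22 participants, pre-existing drops can be found by hand. This stands, and a reader might otherwise infer that pre-existing drops are invisible; they are not. But a mean by visit does not say how many people crossed the threshold, a fall in standing pressure is not a postural drop, and searching a listing is not a planned summary.

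**The rule is not peculiar to vital signs.** Liver tests (16.2) and the C-SSRS categories (16.6) are also counted at any post-baseline visit. That is right, so the ECG contrast shows what the SAP can do and does not show that vital signs alone depart from a convention.

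**The absence of a baseline column is inferred.** Table shells are not in the documents. The titles of the haematology and biochemistry PCS tables specify post-baseline results, whereas the title of Tables 14.3.4.2A/B does not. The point therefore rests on the 16.4 text. If a baseline column is intended, 16.4 should say so.

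**The consequence is limited.** The primary endpoint is TEAEs, the secondary vital-sign endpoint is change from baseline, and clinically significant readings are captured as adverse events. None depends on this row, which is headed as observed values and not as treatment-emergent.

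**Some cases may be screened out.** Exclusions 2 and 16 could remove participants with significant disease, but neither sets an orthostatic threshold.

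**Conclusion.** The point holds as a gap in one safety summary. The post-baseline orthostatic count has no stated baseline count and no split by baseline status, so in this single-arm study it cannot separate pre-existing from new postural drops. That follows from the text and needs no assumed rate.

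The size does need assumptions. With 20% persistent drops and 5% chance per visit, roughly two thirds of the Part A count and half of the Part B count were already positive at baseline. These figures are illustrative: neither rate is in the documents, persistence is taken as certain, visits are taken as independent, and the 'and' and 'or' rows are not modelled separately.

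Two stronger readings are not supported:
- A reader might infer that the planned count overstates new cases by the full gap from 31.4% to 6.4% in Part A. That gap combines three changes: removing prevalent cases, requiring four clean pre-dose visits, and dropping follow-up. With the SAP's own single baseline and all post-baseline visits, the new-onset figure is 10.8%.
- A reader might infer that a new-onset rule makes Parts A and B comparable. It does not, since the relative gap grows from 1.31 to 1.90. The SAP plans separate tables for the two parts and states no comparison between them.

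**What to change.** In SAP 16.4 and Tables 14.3.4.2A/B, for the orthostatic rows:

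1. Add a baseline count, as 16.5 does for ECG.
2. Show post-baseline occurrence by baseline status, as a shift table or a new-onset row, using the SAP baseline (last non-missing pre-dose value). A row for participants who met the criterion at no pre-dose visit can be added as a stricter option.
3. Show on-treatment visits (Days 7 and 14 in Part A; Days 7 to 28 in Part B) separately from follow-up visits (Day 28 in Part A; Days 35 and 42 in Part B).
4. Keep the existing any-post-baseline row.
5. State that counts are to be read within each part, or that any comparison between parts uses Days 7 and 14 only.
6. State whether the 1-minute reading, the 3-minute reading or either one triggers the flag, since 16.4 leaves this open and baseline status needs the same rule.

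The cost is SAP wording and a few columns in existing tables, from data already collected. The drawback is small cells: with 11 and 22 planned participants the split should be shown as counts and read descriptively. One baseline reading will also miss some intermittent pre-existing drops, so the split reduces the mixing without removing it entirely.

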12.1.5. Electrocardiogram

A 12-lead ECG will be performed at the time points described in [Table 2](#). At each time point, the ECGs will be recorded in triplicate at 1-minute intervals. The standard intervals (heart rate, PR, QRS, QT, and QTcF) as well as any rhythm abnormalities will be recorded.

Electrocardiograms will be performed after the participant has been resting in a supine position for at least 5 minutes. When ECG measurements coincide with safety assessments, vital signs assessment or blood draws, procedures should be carried out in said order (vital signs, ECG, blood draw).

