16.1 Adverse Events

TEAEs are defined as any AEs with an onset date on or after the date of the first dose of IP or any worsening of a preexisting medical condition/AE with onset after the start of IP and throughout the study. An AE leading to treatment discontinuation is defined as an AE with action taken of investigational product as Drug Withdrawn. AEs will be coded using the Medical Dictionary for Regulatory Activities MedDRA version 23.0u.

An overall summary of TEAEs, including the number of events, reported, the number and percentage of participants reporting at least one TEAE, the number and percentage of participants reporting at least one related TEAE, the number and percentage of participants by maximum severity, the number and percentage of participants discontinuing due to an adverse event, the number and percentage of participants with at least one serious adverse event, and the number and percentage of deaths will be presented.

A breakdown of the number and percentage of participants reporting each adverse event, categorized by System Organ Class (SOC) and preferred term (PT), will be presented. Note that counting will be by participant, not event, and participants are only counted once within each SOC and PT.

A further tabulation of these data, categorized by relationship (to SAGE-718), will be presented. Participants with multiple events within a particular body system or preferred term will be counted under the category of their drug-related event (related and not related) within SOC and PT. Relationship to SAGE-718 is categorized as related or not related.

A summary of events reported, categorized by severity, will also be provided. Participants with multiple events within a particular SOC and PT will be counted under the category of their most severe event in the following order: severe > moderate > mild within that SOC and PT.

A summary of adverse events leading to discontinuation of SAGE-718 will be provided, grouped by body system and preferred term.

All adverse events (including non-treatment-emergent events) recorded on the CRF will be listed.

Handling of missing AE start dates is defined in Appendix 3. Missing data for severity or relatedness to treatment will not be imputed.

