Table 14.3.3.3.1A	Urinalysis Results by Time Point Part 1 Continuous Variables - Part A	Safety Analysis Set
Table 14.3.3.3.1B	Urinalysis Results by Time Point Part 1 Continuous Variables - Part B	Safety Analysis Set
Table 14.3.3.3.2A	Urinalysis Results by Time Point Part 2 Categorical Variables - Part A	Safety Analysis Set

Table 14.3.3.3.2B	Urinalysis Results by Time Point Part 2 Categorical Variables - Part B	Safety Analysis Set
Table 14.3.4.1A	Vital Sign Results by Time Point - Part A	Safety Analysis Set
Table 14.3.4.1B	Vital Sign Results by Time Point - Part B	Safety Analysis Set
Table 14.3.4.2A	Potentially Clinically Significant Vital Sign Results - Part A	Safety Analysis Set
Table 14.3.4.2B	Potentially Clinically Significant Vital Sign Results - Part B	Safety Analysis Set
Table 14.3.5.1A	Electrocardiogram Results - Part A	Safety Analysis Set
Table 14.3.5.1B	Electrocardiogram Results - Part B	Safety Analysis Set
Table 14.3.5.2A	Overall Electrocardiogram Interpretations by Investigator over Time Point - Part A	Safety Analysis Set
Table 14.3.5.2B	Overall Electrocardiogram Interpretations by Investigator over Time Point - Part B	Safety Analysis Set
Table 14.3.5.3A	Potentially Clinically Significant Electrocardiogram Results - Part A	Safety Analysis Set
Table 14.3.5.3B	Potentially Clinically Significant Electrocardiogram Results - Part B	Safety Analysis Set
Table 14.3.6A	Summary of Columbia–Suicide Severity Rating Scale (C-SSRS) Suicidal Ideation and Suicidal Behavior - Part A	Safety Analysis Set
Table 14.3.6B	Summary of Columbia–Suicide Severity Rating Scale (C-SSRS) Suicidal Ideation and Suicidal Behavior - Part B	Safety Analysis Set

Listing 16.1.7	Subject Enrollment	All Screened subjects
Listing 16.2.1.1	Completion/Discontinued Subjects from Study	Safety Analysis Set
Listing 16.2.1.2	Completion / Discontinuation of Investigational Product (IP)	Safety Analysis Set
Listing 16.2.2	Protocol Deviations	Safety Analysis Set
Listing 16.2.3.1	Subject Analysis Sets	All Enrolled Subjects
Listing 16.2.4.1	Demographic and Baseline Data	Safety Analysis Set
Listing 16.2.4.2	General Medical History	Safety Analysis Set
Listing 16.2.4.3	Prior and Concomitant Medications	Safety Analysis Set
Listing 16.2.4.4	Prior and Concomitant Procedures	Safety Analysis Set
Listing 16.2.5.1	Administration of Investigational Product (Oral)	Safety Analysis Set
Listing 16.2.5.2	Drug Accountability	Safety Analysis Set
Listing 16.2.5.3	Treatment Adherence	Safety Analysis Set

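### The ECG interpretation tables can count one participant as both normal and abnormal at the same time point, so the normal row need not mean a normal ECG (minor)

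*SAP*

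**What the plan says.** Protocol Section 12.1.5 sets the recording scheme: "At each time point, the ECGs will be recorded in triplicate at 1-minute intervals". SAP Section 16.5 repeats it ("Supine 12-lead ECGs will be performed in triplicate") and makes the single tracing the unit that is rated: "Each ECG is evaluated as 'normal', 'abnormal, not clinically significant' and 'abnormal, clinically significant".

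The same section then defines what is tabulated, at baseline and at each scheduled post-baseline time point: a count and percentage of those with "at least one of the triplicate values in the categories of normal", and likewise for the two abnormal categories. The output is Tables 14.3.5.2A and 14.3.5.2B in SAP Appendix G; the Part A title is "Overall Electrocardiogram Interpretations by Investigator over Time Point - Part A".

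The only rule for reducing a triplicate is for the measured intervals: "The average of the triplicate values will be used in the summary, including baseline ECG values". An average cannot be taken of a category. Neither the SAP nor the protocol gives a hierarchy, a majority rule or a derivation of an overall reading. Protocol Section 13.6.5 plans only a listing of ECG findings by participant and visit.

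Elsewhere the SAP does assign one category per participant. In the adverse event severity table of Section 16.1, participants with several events are "counted under the category of their most severe event in the following order: severe > moderate > mild".

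**The concern.** An at-least-one rule suits an abnormal category, because it catches any abnormality. Applied to the normal category it does the reverse: one normal tracing out of three is enough to be counted as normal. The two abnormal rows overlap as well, since a participant with one clinically significant tracing and one that is abnormal but not clinically significant enters both.

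The reader of these tables will want the share of participants with a normal ECG at baseline and at each visit. The normal row does not give that share. A participant who goes from three normal tracings at baseline to one normal and two abnormal on treatment stays in the normal row, so the change in that row from visit to visit does not register the new finding.

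The split between normal and abnormal not clinically significant is what these tables add to the other outputs. Exclusion criterion 15a removes people with a clinically significant ECG finding at Screening or Baseline. Under Protocol Section 12.2.1, ECG changes that the investigator considers clinically significant are recorded as adverse events. SAP Table 7 covers QTcF only. The rule blurs that split.

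**Working it through.** The plan states no figure to reproduce; this is a check of a counting rule.

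**Inputs.** Three tracings per time point (Protocol 12.1.5, SAP 16.5). Three mutually exclusive ratings per tracing (SAP 16.5). Planned N of 11 in Part A and 22 in Part B (SAP 10.1). All three tracings are taken as evaluable.

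**Counting.** At one time point let

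- m = participants with all three tracings abnormal,
- k = participants with both normal and abnormal tracings,
- j = participants with tracings in both abnormal categories.

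Then:

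- Normal row under the SAP rule = N − m.
- Participants with three normal tracings = N − m − k.
- Excess in the normal row = k, never negative.
- The not-clinically-significant row exceeds its worst-of-three count by j.
- The clinically significant row is the same under either rule, because at least one such tracing and a worst tracing of that kind are the same event.
- Sum of the three rows = 100 × (N + k + j)/N percent.

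Each mixed participant therefore adds 1/11 = 9.1 points to the normal row in Part A and 1/22 = 4.5 points in Part B.

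**Illustration with m = 1 and j = 0** (hypothetical counts):

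| k | Part A normal, SAP rule | Part A three normal | Part A row sum | Part B normal, SAP rule | Part B three normal | Part B row sum |
|---|---|---|---|---|---|---|
| 0 | 10/11 = 90.9% | 10/11 = 90.9% | 100% | 21/22 = 95.5% | 21/22 = 95.5% | 100% |
| 1 | 90.9% | 9/11 = 81.8% | 109.1% | 95.5% | 20/22 = 90.9% | 104.5% |
| 2 | 90.9% | 8/11 = 72.7% | 118.2% | 95.5% | 19/22 = 86.4% | 109.1% |
| 3 | 90.9% | 7/11 = 63.6% | 127.3% | 95.5% | 18/22 = 81.8% | 113.6% |

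The SAP's normal percentage does not move with k.

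**Range under assumed rates.** The documents do not say how often three readings disagree. Let q be the probability that a tracing is abnormal and ρ the correlation between readings in the same triplicate, both assumed. Two readings disagree with probability 2q(1 − q)(1 − ρ). In a mixed triplicate exactly two of the three pairs disagree, so

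P(mixed) = (3/2) × 2q(1 − q)(1 − ρ) = 3q(1 − q)(1 − ρ).

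Excess in the normal row, in percentage points:

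| q | ρ = 0 | 0.5 | 0.8 | 0.95 | 1 |
|---|---|---|---|---|---|
| 0.10 | 27.0 | 13.5 | 5.4 | 1.35 | 0 |
| 0.20 | 48.0 | 24.0 | 9.6 | 2.40 | 0 |
| 0.30 | 63.0 | 31.5 | 12.6 | 3.15 | 0 |

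Check with a beta-binomial at q = 0.20, ρ = 0.5: P(three normal) = 0.8 × 1.8 × 2.8/6 = 67.2%; P(three abnormal) = 0.2 × 1.2 × 2.2/6 = 8.8%. The SAP's normal row would show 100 − 8.8 = 91.2%, and the excess is 91.2 − 67.2 = 24.0 points, as in the table. The expected number of mixed participants is 0.24 × 11 = 2.6 in Part A and 0.24 × 22 = 5.3 in Part B.

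**The case against.** The strongest reply is that the row is correct as defined and that nothing important is lost. Much of this stands.

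- A reader might infer that the rule hides abnormal ECGs. It does not. Anyone with an abnormal tracing is counted in an abnormal row of the same table, and the clinically significant row is unchanged by any worst-of-three rule.
- A reader might infer that the secondary endpoint is compromised. That endpoint is change from baseline in ECGs. It is served by the averaged intervals, their changes, and the QTcF criteria in SAP Table 7, none of which use the category rule.
- A reader might take a large overstatement as established. The upper end of 63 points needs 30% of tracings abnormal and three readings, taken a minute apart in one supine person, that are independent of each other. High agreement is more plausible, and the excess is then a few points or nil. The rows can exceed 100%; they need not.
- The data remain visible. ECG findings are listed by participant and visit, and with 11 and 22 planned participants the listings can be read directly.
- The word overall in the table title might mean that the investigator gives one reading per time point. If the case report form collects it that way, the overlap disappears. The case report form is not among the documents, however, and SAP Section 16.5 says that each ECG is rated and that any one of the three suffices.

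The reply does not remove the defect. A row labelled normal will be read as participants with a normal ECG, and the planned text provides no footnote to prevent that. The SAP's own severity rule in Section 16.1 shows that the double counting is not a convention of the plan.

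**Conclusion.** The point holds as a minor one. The rule in SAP Section 16.5 allows a participant to be normal and abnormal, or in both abnormal categories, at the same time point. The normal count then exceeds the number with three normal tracings by exactly the number with mixed normal and abnormal readings. That relation follows from the text and needs no assumption beyond three evaluable tracings.

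The size does rest on assumptions. Per participant it is fixed by the planned N, and actual enrolment would change the denominators. In total it depends on a discordance rate that the documents do not give, and it can be zero.

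The consequence is confined to the normal and not-clinically-significant rows of descriptive Tables 14.3.5.2A/B. The documents do not support any claim that a safety signal is lost or that the primary or secondary endpoint analyses are affected.

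**What to change.** In SAP Section 16.5, replace the at-least-one rule with one classification per participant per time point: the worst of the evaluable tracings, in the order abnormal clinically significant > abnormal not clinically significant > normal. State that normal then means that all evaluable tracings were normal. Repeat this as a footnote to Tables 14.3.5.2A and 14.3.5.2B. The rows will then sum to 100% of participants with an evaluable ECG at that time point.

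Defining normal as all tracings normal, and leaving the rest as it is, would repair the normal row but not the overlap between the two abnormal rows.

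The cost is one sentence, one footnote and a small programming change, with no new data. If the database is already locked, SAP Section 6.0 provides for describing the change and its justification in the clinical study report. A shift table from baseline category to worst post-baseline category would be a useful option, but the protocol does not call for one for ECG and the correction does not depend on it.
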